12.5.2.4 Summary descriptions and listings

The 28-day average daily spasm count, change from baseline and relative change from baseline will be summarized by treatment arm for each 28-day period.

The above summary will be repeated for the subgroups presented in Table 9.3-2.

Boxplot of 28-day average daily spasm count and change from baseline in 28-day average daily spasm count will be plotted by treatment arm.

A cumulative distribution function (CDF) plot, based on the three 28-day periods, on respectively observed, change from baseline and relative change from baseline in daily spasm count will be provided.

A patient listing for 28-day average daily spasm count on observed, change from baseline and relative change from baseline along with responder status (as defined in Section 10.17) will be presented.

12.5.3 Secondary Efficacy Endpoint

The family-wise Type 1 error related to the primary endpoint and the secondary efficacy endpoint will be controlled at 2-sided 0.05 level by a hierarchical testing procedure.

For comparison of nabiximols treatment arm versus placebo treatment arm, if the primary endpoint is significant, the statistical test will be performed. The Type I error rate for comparing nabiximols treatment arm to placebo treatment arm for the secondary endpoint will be controlled at the nominal 0.05 level (2-sided). The statistical test between nabiximols treatment arm and placebo treatment arm will be performed and inference will be provided. Otherwise, if primary endpoint does not reach the statistical significance at the nominal Type I error rate, p-value will be calculated but no claim could be made based on that p-value as per testing strategy described above.

12.5.3.1 Primary Analyses

The MSSS-88 is a patient self-report measure of the impact of spasticity (muscle stiffness and spasms) in MS. It is composed of 88 items ranging from 1 (not at all bothered) to 4 (extremely bothered).

The secondary efficacy endpoint, change from baseline to Week 12 in of the MSSS-88 total score (as defined in Section 10.18) will be analyzed on patients belonging to the FAS, during the 12-week randomized period (see Section 10.2.2) using the same MMRM approach as the one applied to the primary efficacy estimand (as described in Section 12.5.2.1). However, the timepoint effect will have 2 levels: Week 8 and Week 12.

The comparison between nabiximols treatment arm and placebo treatment arm will be performed following the testing procedure outlined above and assesses the secondary estimand (as defined in Section 9.1).

Additionally, LS means change from baseline and 95% CI at Week 8 and Week 12 per treatment arm will be plotted.

12.5.3.2 Sensitivity Analyses

Sensitivity analyses will be carried out to assess the robustness of the results of the primary efficacy analysis for the secondary estimand with regard to i) the assumption that missing data are MAR and ii) the assumption that the residuals from the fitted model are from a normal distribution.

12.5.3.2.1 Missing at random assumption

To assess the robustness of the treatment effect with regard to missing data, sensitivity analyses based on a MNAR MI model using a placebo-based multiple imputation approach (as described for primary endpoint in Section 12.5.2.2) will be conducted using FAS during the 12-week randomized period (as defined in Section 10.2.2.

12.5.3.2.1.1 MI models - General consideration

The same indicator variables as presented for the primary endpoint will be used (see Section 12.5.2.2.1.1)

Back up models may be implemented if any imputation model has a non-convergence issue due to sparse data or a memory space issue, removing randomization strata as described in Section 12.0.

Each imputation model will use a common random seed value of 20220312 apart for the MCMC stage for which the random seed number will be 20220318. Furthermore, any imputed value below -351 will be set to -351 and any imputes value above 353 will be set 353 to account for the range of change in score.

Each imputed dataset will be analyzed using the same MMRM as the one used to assess the primary analysis (as described in Section 12.5.3.1).

12.5.3.2.1.2 Missing data description

Description of missing data patterns will present the number and percentage of patients within each missing data pattern by treatment arm for the MSSS-88 total score (as defined in Section 10.18).

Description of MSSS-88 total score monotone missing pattern will be performed by treatment arm, presenting the number and percentage of patients within each of the following monotone missing data pattern:

- Pattern 1: Patient with no baseline score
- Pattern 2: Patient with a baseline score but no post-baseline scores
- Pattern 3: Patient with a baseline score and a Week 8 score only
- Pattern 4: Patient with a baseline score and score up to Week 12

This summary will also provide Mean (SD) at Baseline, Week 8 and Week 12 for each monotone missing data pattern.

Graphical summary of missing data pattern presenting by treatment arm

- MSSS-88 total score mean (±SD) at baseline, Week 8 and Week 12
- Change in MSSS-88 total score mean (±SD) from baseline to Week 8 and Week 12

will also be provided.

12.5.3.2.1.3 Monotone missing data pattern

1,000 monotone datasets will be obtained using the same approach as the one used to analyze average daily spasm count (as described in Section 12.5.2.2.1.1.4). However, the MCMC model used to analyze the MSSS-88 total score will include factor and covariate in the following order, indicator variables for randomization strata of region and prior cannabis use and for treatment arm as well as baseline MSSS-88 total score for each Week (i.e. Week 8, Week 12).

12.5.3.2.1.4 Pattern Mixture Model Placebo-based Multiple Imputation method

Using the same approach as the one used for primary endpoint (as described in Section 12.5.2.2.1.1.5), a pattern mixture placebo-based multiple imputation method will be implemented using baseline MSSS-88 total score to predict Week 8 and Week 12 MSSS-88 total score in a MNAR model.

However, at Step 2

- For patients from nabiximols treatment arm who withdraw from the study due to a reason not related to COVID-19 with non-missing MSSS-88 total score but non-intermittent missing Week t (eg Week 8, Week 12) MSSS-88 total score, the active arm baseline will be used to predict each missing Week t MSSS-88 total score using non missing baseline and Week t MSSS-88 total score from patients on placebo treatment arm. The indicator representing randomization strata will be included in modelling the MNAR process in the same order as presented in Section 12.5.3.2.1.3. Therefore, the model used to generate nabiximols Week t MSSS-88 total score will include, in the following order, indicator variables representing randomization strata of region and prior cannabis use, and baseline MSSS-88 total score.
- While for patients on the nabiximols treatment arm who withdraw from the study due to a reason related to COVID-19 or for patients on the placebo arm with non-missing baseline MSSS-88 total score, but non-intermittent missing post baseline MSSS-88 total score at Week t (eg, Week 8, Week 12), and separately for each treatment arm, missing MSSS-88 total score will be imputed sequentially at each assessment using a MAR imputation based on all non-missing MSSS-88 total score from that Week and data from prior Week (after imputation). The indicator variables for randomization strata of region and prior cannabis use will be included in modelling of the MAR process in the same order as presented in Section 12.5.3.2.1.3. Therefore, the model used to generate Week 12 MSSS-88 total score will as baseline MSSS-88 total score as well as Week 8 MSSS-88 total score.

12.5.3.3 Supplemental Analyses

12.5.3.3.1 Impact of intercurrent events

12.5.3.3.1.1 Impact on treatment discontinuation

The robustness of the treatment effect with regards to off-treatment data (IMP discontinuation) will be assessed as follows:

• The change from baseline to Week 12 will be analyzed on the FAS using the same MMRM model as the one used to analyze the secondary estimand (see Section 12.5.3.1) but during the 12-week on-treatment period (as defined in Section 10.2.2) using on-treatment MSSS-88 total score assessments.

12.5.3.3.1.2 Impact on major important protocol deviation

If more than 10% of patients from FAS are excluded in the PP Analysis Set; the robustness of the MSSS-88 total score with regard to major IPDs will be assessed as follow. The change from baseline to Week 12 will be analyzed during the 12-week randomized period (as defined in Section 10.2.2), using the same MMRM model as the one used to analyzed the secondary estimand (see Section 12.5.3.1) but using the PP analysis set.

12.5.3.3.1.3 Impact on COVID-19

If at least 5 patients have at least one MSSS-88 assessment impacted by COVID-19, as assessed by the investigator, the impact of COVID-19 on the treatment effect will be assessed on MSSS-88 total score by analyzing the change from baseline to Week 12 on FAS during the 12-week randomized period (as defined in Section 10.2.2), using the same MMRM model as the one used to analyze the secondary estimand (see Section 12.5.3.1) but removing that patients having at least one visit impacted by COVID-19.

12.5.3.4 Summary description and Listings

The MSSS-88 total score along with the 8 subscale scores (as described in Section 10.18) will be summarized by treatment arm using classical descriptive statistics (as defined in Section 12.0) but also presenting the floor and the ceiling effect defined by the number (percentage) of patients scoring the worst possible (floor effect) and the best possible (ceiling effect).

Additionally, using the ALPHA option along with the NOMISS option of the SAS® CORR procedure, the internal consistency of each score will be assessed using the Cronbach's alpha coefficient.

Boxplot of total score and change from baseline in total score by treatment arm will be presented by Week.

CDF plot of change from baseline to Week 12 value will be plotted by treatment arm.

A by-patient listing presenting the MSSS-88 total score along with the 8 subscale scores (as described in Section 12.5.4.1) and their corresponding change from baseline value will be provided.

12.5.4 Exploratory Efficacy Analyses

12.5.4.1 The MS Spasticity Scale

The 88 items of the MSSS-88 scale (as presented in Section 12.5.3.1) are grouped to derive 8 subscales (as defined in Section 10.18) within 3 different categories which are composed of: 3 spasticity symptoms (i.e., muscle stiffness, pain and discomfort, muscles spams), 3 areas of physical functioning (i.e., effects on daily activities, ability to walk, body movement) and 2 areas of psychosocial impact (i.e., emotional health and social functioning).

The same approach as the one used to analyze the MSSS-88 will be applied as primary analyses of each of the 8 sub-scores (as described respectively in Section 12.5.3.1).

12.5.4.2 NRS for spasm severity

The NRS spasm scale is ranging from 0 (no spasms) to 10 (Worst possible spasm) to assess the overall severity of spasm in patients with MS during the last 24 hours.

The exploratory efficacy endpoint, change from baseline to Week 9 to 12 in 28-day average NRS spasm severity score (as defined in Section 10.19) will be analyzed on patients belonging to the FAS, during the 12-week randomized period (see Section 10.2.2) using the same MMRM approach as the one applied to the primary efficacy estimand (as described in Section 12.5.2.1).

The average NRS spasm severity score and change from baseline score, will be summarized by treatment arm for each 4-weekperiod.

A by-patient listing presenting the average NRS spasm severity scores for the 12-week randomized period and the follow-up period will be provided.

12.5.4.3 NRS for spasticity

The NRS spasticity scale is ranging from 0 (no spasticity) to 10 (worst possible spasticity) to assess the overall spasticity in patients with MS during the last 24 hours.

The exploratory efficacy endpoint, change from baseline in 7-day average daily NRS spasticity score (as defined in Section 10.4.1) compared to the 7-day daily NRS spasticity score from Day 78 to Day 84 (as described in Section 10.20).

This exploratory endpoint will be analyzed on patients belonging to the FAS, during the 12-week randomized period (see Section 10.2.2) using the same MMRM approach as the one applied to the primary efficacy estimand (as described in Section 12.5.2.1). However, the timepoint effect will have 12 levels: Week 1 through to Week 12 (as defined in Section 10.20).

The average NRS for spasticity score and change from baseline score, will be summarized by treatment arm for each 1-week period 1 (as defined in Section 10.20)

A by-patient listing presenting the average NRS spasm spasticity scores for the 12-week randomized period and the follow-up period will be provided.

12.5.4.4 Timed 25-foot Walk

A decrease in average time to complete the two trials will show an improvement.

The change from baseline to Week 12 in average timed 25-foot walk (as described in Section 10.5) will be analyzed during the 12-week randomized period using ANCOVA performed with the SAS® MIXED procedure.

This model will include all patients belonging to the FAS with a baseline average T25FW (as defined in Section 10.4.1) and at least one post-baseline average T25FW value (as described in Section 10.21). In case of premature study discontinuation before Week 12, averageT25FW values will be imputed using a last observation carried forwards (LOCF) methodology.

The preferred model will include the fixed categorical effects of treatment arm, randomization strata of prior cannabis use and randomization strata of region as well as, the baseline average T25FW as covariate.

The treatment arm will have 2 levels: nabiximols and placebo.

The randomization strata of prior cannabis use will have 2 levels: Yes and No.

The randomization strata of region will have 2 levels: USA and non-USA.

Stratification classification will be obtained from the 'Randomization eCRF' page as this will show the true classification in case of mis-stratification.

This model will provide the LS mean estimates for each treatment arm, along with the standard errors and 95% confidence intervals (CIs) as well as, the least squares mean estimates of the mean treatment difference in change from baseline in average T25FW with the standard error of the difference and 95% CI. T-statistics corresponding to the Type III sum of squares for difference in LS means will be used to obtained nominal p-value for treatment arm comparison at Week 12.

In case of non-convergence of the preferred model or memory space issue a back-up model will be used removing some of the randomization strata as mentioned in Section 12.0.

Additionally, a plot of LS mean change from baseline and corresponding 95% CI at Week 12 per treatment arm.

Descriptive statistics for the average T25FW values and change from baseline by treatment arm will be provided. A by-patient listing presenting observed and derived variables will be presented.

A patient listing presenting observed and derived variables will be presented.

12.5.4.5 Modified Ashworth Transformed Score

Modified Ashworth Scale (MAS) Transformed Score was planned to be conducted and scored on 10 lower limb muscle groups (hip flexors and adductors, knee flexors and extensors, and plantar flexors) on the left and the right side of the body at Baseline (Day 1) and Week 12 (or early withdrawal) for all patients having given their informed consent before Protocol Version 5 was approved. This assessment was removed in Protocol Version 5.

Consequently, no statistical analysis, description or listing will be performed on MAS scores thus no dedicated ADaM will be programmed. However, corresponding SDTM will be created.

12.6 Quality of life

12.6.1 36-items Short Form Survey (SF-36)

The SF-36 version 2 is a health-related quality of life (HRQOL) questionnaire. It is composed of 36 items used to derive 8 domain scale scores (concepts) ranging for 0 to 100% and two component summary measures (as described in Section 10.22). For each domain score/component summary higher score/measure is representing better health.

All the analyses and summaries will be performed using the FAS during the 12-week randomized period.

The change from baseline to Week 12 (LOCF) of each of the 8 domain scale scores and the 2 component summary measures (as described in Section 10.5) will be analyzed during the 12-week randomized period by an ANCOVA model performed with the SAS® MIXED procedure using the same approach as the one described in Section 12.5.4.4.

The profile of scores will be illustrated by a plot presenting LS mean (± 95% CI) change from baseline to Week 12 by treatment arm of each of the 10 domain scale/component summary scores.

The 8 domain scale scores and the 2 component summary measures will also be summarized by treatment arm at baseline, Week 12 (LOCF) and on change from baseline to Week 12 (LOCF) using classical descriptive statistics as described in (Section 12.0).

The floor and the ceiling effect defined by the number (percentage) of patients scoring the worst possible (floor effect: 0) and the best possible (ceiling effect: 100%) will be also provided for the 8 domain scale score.

Additionally, the internal consistency of each domain scale score (derived from more than 2 items) will be assessed using the Cronbach's alpha coefficient (as described in Section 12.5.3.4).

Furthermore, the Self-Evaluated Transition domain score will be also evaluated using a shift table from baseline to Week 12 (LOCF).

A patient listing presenting observed and derived variables will be presented.

12.7 PK Analyses

Plasma concentrations will be obtained for THC and its relevant metabolites (11-OH-THC and 11-COOH-THC) and CBD and its relevant metabolites (7-OH-CBD and 7-COOH-CBD).

- at Day 1 and Day 15, Day 29 or Day 75 pre-dose and at 3 different post dose timepoints as described in Table 10.2-2 for those patients following a semi-intensive PK draw assessment
- at Day 1 pre-dose and at any time during Day 15, Day 29, Day 57 and Day 85 as described in Table 10.2-3 for those patients undergoing a sparse PK draw assessment

Concentration data will be summarized separately for sparse and semi-intensive regimen by analysis visit and predefined timepoint (semi intensive regimen only) as described respectively in Table 10.2-3 and Table 10.2-2.

Concentrations that are below the limit of quantification (BLQ) will be excluded from the computation of descriptive statistics but the number of patients presenting a concentration below the limit of quantification will be presented at each time point. The number of observations, mean, standard deviation, geometric mean, geometric standard deviation, coefficient of variation (%), median, minimum, maximum values will be displayed.

Individual data will be presented in listing.

If concentration data show that sufficient systemic exposure for THC or one or more of the metabolites is available, relevant PK parameters may be calculated using a population PK model. In that case, PK modeling will be presented a stand-alone report.

12.8 Safety Analyses

The safety analyses will be conducted during the 12-week on-treatment period (as defined in Section 10.2.2). All safety analysis will be performed by actual treatment arm (as defined in Section 9.4.1) using the SAF.

Some analyses of adverse events and laboratory parameters will assess the potential impact of IMP among the subgroups presented in Table 9.3-3.

12.8.1 Adverse Events

Adverse events will be coded using MedDRA 23.0 or higher according to the version in use at time of database lock. All safety analyses will be performed by actual treatment arm and reported using the SAF. A TEAE is one that started, or worsened in severity or seriousness, following the first dose of IMP. Any adverse event that worsens or becomes serious after the first IMP dose are recorded as a separate AE, therefore for programming purposes an AE will be classified as a TEAE if it first occurs on or after the IMP Start Date and before the IMP End Date + 30 days.

All AEs will be classified during the pre-treatment period, the 24-week on-treatment period or during the follow-up period as follows:

- Events that occurred before IMP Start Date are classified as pre-treatment AEs
- Events that occurred between IMP Start Date and 30 days after IMP End Date are considered on-treatment and classified as treatment-emergent AEs (TEAEs)
- Events occurring more than 30 days after IMP End Date are classified as follow-up AEs.

The following counting rules will be applied:

- For incidence reporting, if a patient reported more than one AE that was coded to the same preferred term/system organ class within a given treatment arm, the patient will be counted only once for that specific preferred term/system organ class by treatment arm and the rules defined below will be applied.
- For TEAEs presented by action taken on IMP, the worst action taken among the events with same SOC/PT will be selected for each patient. If action taken is missing for a TEAE, the action taken "drug withdrawn" will be assigned considering the AE leads to permanent IMP discontinuation. The imputed values for action taken will be used for incidence summaries, while the actual values will be used in data listings.
- For TEAEs presented by severity, the worst severity among the events with same SOC/PT will be selected for each patient. If the severity is missing for a TEAE, then a severity of "Severe" will be assigned. The imputed values for severity assessment will be used for incidence summaries, while the actual values will be used in data listings.
- For TEAEs presented by relationship to IMP, the relationship to IMP, as assigned by the investigator, for each event during the clinical trial will be presented for each patient. If the relationship to investigational product is missing for a TEAE, a causality of "Related" will be assigned. The imputed values for relationship assessment will be used for incidence summaries, while the actual values will be presented in data listings.
- For TEAEs presented by categories for time of first onset of AE, if the AE start date is missing, it will be imputed as specified in Table 10.23-1 for AE summary but actual values will be presented in data listing.

For the purpose of inclusion in TEAE tables, incomplete AE onset dates will be imputed as specified in Table 10.23-1. No duration will be calculated for adverse events with incomplete start or stop dates, or for ongoing adverse events.

The following denominators will be used for percentages:

• For summary by SOC and PT the denominator to derive the percentage will be the number of patients in the treatment arm.

- For subgroup analysis by SOC and PT the denominator to calculate the percentage will be the number of patients in the treatment arm and in the category of the analyzed subgroup.
- For summary by SOC and PT and category of time to first onset of AE the denominator to derive the percentage will be the number of patients at risk in the treatment arm for in each time interval category.
- For summary by SOC and PT and category of duration of AE the denominator to derive the percentage will be the number of patients in the treatment arm in each time interval category.

All summary by SOC and PT will be sorted by internationally agreed SOC order then, PT will be presented by alphabetical order.

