#### 12.5 Causality Assessment

Causality assessment is required for all AEs and SAEs. Causality assessment must only be assigned by the investigator. All cases judged as having a reasonable suspected causal relationship to the IMP must be reported as such. The expression *"reasonable causal relationship"* is meant to convey in general that there are facts (evidence) or arguments to suggest a causal relationship.

The following question, which must be answered by the investigator for all AEs, is used to capture the reasonable causal relationship of an event to the IMP:

"In your opinion is there a plausible relationship to the IMP?" The answer is either "yes" or "no."

Events that start before the first dose of IMP (pretreatment) should be considered as not causally related. Where a pre-treatment event worsens in severity following the first dose of IMP, a new event record should be entered into the eCRF.

Considering the explanation given above, investigators are strongly encouraged to express their opinion on what the cause of an AE might be. For individual patients, the investigator is usually in the best position to assess the underlying suspected cause of an AE. For all AEs and especially SAEs, it is important that the investigator assess not only the possible role of the IMP but also other potential contributing factors. Factors for consideration of the underlying cause may include the following:

- Medical and disease history
- Lack of efficacy/worsening of treated condition
- Concomitant or previous treatment
- Withdrawal of IMP
- Protocol-related procedure

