#### D) Severity

When describing the severity of an AE, the terms mild, moderate, or severe should be used. Clinical judgment should be used when determining which severity applies to any AE.

If the severity of an AE fluctuates day-to-day, e.g., a headache or constipation, the change in severity should not be recorded each time; instead, only the worst observed severity should be recorded with AE start and stop dates relating to the overall event duration, regardless of severity.

A severe AE is not the same as an SAE. For example, a patient may have severe vomiting, but the event does not result in any of the SAE criteria above. Therefore, it should not be classified as serious.

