#### 13.6.5.2 Adverse Events

AEs will be coded according to the MedDRA.

A TEAE is one that started, or worsened in severity or seriousness, following the first dose of IMP.

Descriptive presentations of TEAEs will be given by PT and SOC for the safety analysis set. The number of patients reporting at least 1 TEAE will be provided.

The following summaries will be produced at a minimum:

- All-causality TEAEs
- Treatment-related TEAEs
- All-causality TEAEs by maximal severity
- All-causality serious TEAEs
- Treatment-related serious TEAEs
- TEAEs reported as leading to permanent cessation of IMP
- Fatal TEAEs

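### SAP 12.8.1 flags TEAEs by onset date alone, so a pre-treatment AE that only becomes serious after first dose can be missed from the serious TEAE tables

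*SAP*

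**What the plan says.** Protocol 13.6.5.2 defines the term: "A TEAE is one that started, or worsened in severity or seriousness, following the first dose of IMP". SAP 12.8.1 repeats this definition and then gives the rule that will be programmed. Its premise is "Any adverse event that worsens or becomes serious after the first IMP dose are recorded as a separate AE", and the rule that follows is "for programming purposes an AE will be classified as a TEAE if it first occurs on or after the IMP Start Date", with an upper limit of 30 days after IMP End Date. The complementary class is also set by date: "Events that occurred before IMP Start Date are classified as pre-treatment AEs".

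The recording instruction for sites is in Protocol 12.5: "Where a pre-treatment event worsens in severity following the first dose of IMP, a new event record should be entered into the eCRF". The same section sets a default for causality: "Events that start before the first dose of IMP (pretreatment) should be considered as not causally related". Protocol 12.3 requires SAEs to be entered in the eCRF within 24 hours but does not say that this must be a new record. SAP 6.2 declares no change from the protocol.

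**The concern.** The programmed rule reproduces the protocol definition only if every event that worsens or becomes serious after first dose gets a record with a post-dose start date. The protocol asks for such a record on one of those two triggers, worsening severity. It asks for none when seriousness alone changes.

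The two attributes are separate. Protocol 12.6 D says so directly: "A severe AE is not the same as an SAE". An event can meet a seriousness criterion such as hospitalization without a change of severity grade.

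At stake is the serious TEAE count. Serious events are usually few, so a single misclassified event can be visible in the table, and the safety tables are among the main outputs kept after early termination.

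**Working it through.** No arithmetic applies. The check follows an event through the rules as written.

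**Inputs**
- AE collection runs from after Visit 1 (Protocol 12.6), so it covers the 28 (+2)-day baseline period.
- New-record trigger: Protocol 12.5, severity only.
- TEAE definition: Protocol 13.6.5.2, onset or worsening in severity or seriousness.
- TEAE programming rule: SAP 12.8.1, record start date only.
- Tables affected: SAP 12.8.1.2 (overall summary), 12.8.1.3 and 12.8.2.2 (TEAEs and serious TEAEs by SOC and PT).

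**The cases compared**

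| Event | New record asked for by Protocol 12.5 | Start date used | Class under SAP 12.8.1 | Class under Protocol 13.6.5.2 |
|---|---|---|---|---|
| Starts on or after first dose | Not needed | Post-dose | TEAE | TEAE |
| Starts before dose, severity worsens after dose, not serious | Yes | Post-dose | TEAE | TEAE |
| Starts before dose, severity worsens and becomes serious after dose | Yes | Post-dose | TEAE | TEAE |
| Starts before dose, becomes serious after dose, severity unchanged | No | Pre-dose | Pre-treatment AE | TEAE |

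The rule and the definition disagree only in the last row.

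**One hypothetical event in the last row.** An infection starts in the baseline period, is ongoing on Day 1, and leads to hospitalization on Day 10 with the severity grade unchanged.
1. Protocol 12.5 does not call for a new record.
2. The existing record is updated as serious and keeps its pre-dose start date.
3. SAP 12.8.1 classes it as pre-treatment.
4. It is absent from the overall and serious TEAE counts, although it meets the protocol definition.
5. Its causality falls under the pre-dose default in Protocol 12.5, because there is no post-dose record to carry a separate assessment.

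**What survives in the reporting.** SAP 12.8.1.1 lists all SAEs with start date, seriousness and treatment-emergent status, so the event is visible there under the wrong flag. Table 7-1 of the addendum keeps SAP 12.8.1 and 12.8.2 with named exclusions. The overall and serious TEAE tables are not among those exclusions. The summary of serious TEAEs related to IMP appears to be.

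**The case against.** The strongest reply is that SAP 12.8.1 states a recording convention as fact and that SAP 6.0 says the plan is to be read with CRF V3.0, which is not among these documents. Protocol 12.5 is silent on seriousness and does not forbid a new record. In addition, Protocol 12.1.1 counts worsening of a pre-existing condition as an AE without tying it to the severity grade, and severity is a matter of clinical judgment. A site could therefore re-record such an event, or grade it as worse. This stands as a limit: the omission follows from the protocol as written and is not shown for the actual data. It does not remove the mismatch, because nothing in the documents tells sites to do what the SAP assumes.

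A reader might also infer four stronger points that the documents do not support.
- *The single-record rule in Protocol 12.6 D adds a second route to the loss.* That rule ("only the worst observed severity should be recorded with AE start and stop dates relating to the overall event duration, regardless of severity") covers severity that fluctuates from day to day. It does not address seriousness, and it need not change.
- *The investigator is no longer prompted to consider causality.* Protocol 12.5 requires a causality assessment for all AEs and SAEs and stresses SAEs, and Protocol 12.3 makes pharmacovigilance aware of every SAE. The pre-dose default pulls towards not related, but the prompt remains.
- *All related-event tables are affected.* The addendum appears to drop the serious related summary, so less related-event output is exposed.
- *A number of missed events can be given from the planned 446 patients.* The documents give no rate for pre-treatment AEs ongoing at first dose or for those turning serious. Enrollment stopped short of plan, and events whose severity also worsens are already counted.

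Nor is a distortion between arms shown: the rule is the same for nabiximols and placebo.

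**Conclusion.** The point holds as a narrow definitional mismatch. SAP 12.8.1 relies on a recording practice that Protocol 12.5 requires for severity but not for seriousness. Where that practice is not followed, an event that meets the protocol's TEAE definition is tabulated as pre-treatment.

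The affected set is small: onset before first dose, still ongoing at first dose, newly serious on or after it, severity judged unchanged, and no new record opened. The number of such events cannot be estimated from the documents. Each one lowers the serious TEAE event count by one, and none can raise it.

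The conclusion assumes that CRF V3.0 and any completion guidance do not already require a new record when seriousness changes. If they do, the tables are right and only the protocol wording needs correcting. The event is not lost to safety reporting in either case, since it remains in the SAE listing and is reported to pharmacovigilance.

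**What to change.** In SAP 12.8.1 or the addendum, before unblinding, add a review of every SAE with onset before IMP Start Date. Flag the event as a TEAE if it first met a seriousness criterion on or after IMP Start Date. Use the date of becoming serious from the eCRF or safety database if it is captured. The documents do not show that it is, so provide for blinded manual review otherwise. The addendum is to be approved before unblinding, so the step fits there.

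Align Protocol 12.5 and the eCRF instructions with 13.6.5.2, so that a new record is opened when a pre-treatment event worsens in severity or becomes serious after first dose, and so that this record carries its own causality assessment. With enrollment already halted, this wording change will do little for data already collected. It mainly serves any guidance or later protocol that reuses the text. No change to Protocol 12.6 D is needed.

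The cost is a short blinded review and one extra condition in the TEAE flag. The serious TEAE count may rise slightly.
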